### *6.8 SPG Block Procedure*

Participants will lay supine on an examination table with their chin elevated. Each nares will be visually inspected. A SphenoCath device attached to a 5mL syringe will be coated with a lubricating gel. The SphenoCath catheter tip will be inserted 3-4cm into the left nares, guided above the middle turbinate, and 2.5mL of solution will be deposited. Participants in the treatment arm will receive a 1% lidocaine solution. Participants in the control arm will receive a saline solution. The same process will be repeated in the right nares. The participant will then remain in the same supine position for five minutes before sitting up. Participants will be asked to refrain from using any new as-needed headache treatments for the one week following the procedure.

### *6.9 Outcome measures*

## **A Phase II Randomized Controlled Double-Blind Clinical Trial of Sphenopalatine Ganglion Block for Headache after Concussion**

-Primary outcome data points:

1. Headache severity scores: the patient will be asked to use an online survey to report their average daily headache severity score every 24 hours, starting one week prior to the SPG block procedure, until one week following the procedure. They will be asked to rate their headache on a scale of 0 to 6, with 0 corresponding to “absent” and 6 corresponding to “severe.” Additionally, at the SPG block research visit, the patient will be asked to report a headache severity score immediately before the procedure, 15 minutes after the procedure, and two hours after the procedure.

-Secondary outcome data points:

1. Patient Global Impression of Change (PGIC): a rating scale of global improvement with treatment on which participants use a seven-point scale (“1” = very much improved, “4” = no change, “7” very much worse). Using the online survey, participants will rate their change at two hours and 24 hours following the SPG block procedure.

2. Headache frequency/duration: at baseline prior to the procedure, using the aforementioned online survey, the patient will be asked to report the number of headache episodes and hours with headache every 24 hours over the one week prior to the SPG block. Every 24 hours after the SPG, for up to one week after the procedure, as part of the online survey the patient will be asked to record the number of headache episodes and hours with headache in identical fashion.

3. As-needed headache treatment usage: at baseline prior to the procedure, using the aforementioned online survey, the patient will be asked to report the number of uses of as-needed headache medications used every 24 hours in the one week prior to the SPG block. Every 24 hours after the SPG, for up to one week after the procedure, as part of the online survey the patient will be asked to record the number of uses of as-needed headache medications.

-Exploratory outcome data points:

1. Sport Concussion Assessment Tool Version 5 (SCAT5) symptom scores: A symptom checklist survey from the SCAT5 will be given to the patient at baseline at the beginning of the study and every 24 hours during the study period, until one week following the SPG block procedure. From this checklist, the patient will be asked to rate all 22 symptoms on the checklist as 0 (absent) to 6 (severe).

2. Heart rates: immediately prior to the procedure, and 15 minutes following the procedure, the patients’ heart rates will be recorded in identical fashion using a Polar (Bethpage, NY) chest-worn heart rate monitor. Heart rate and R-R interval will be recorded at rest in the supine position. R-R interval will be recorded for five minutes. Root mean square of successive differences (RMSSD) will be calculated from the R-R interval to measure heart rate variability using Kubios HRV (Kuopio, Finland). Following this, heart rate will be checked immediately upon standing and after standing for two minutes.

*6.10 Schedule of Visits and Testing Requirements:*

## A Phase II Randomized Controlled Double-Blind Clinical Trial of Sphenopalatine Ganglion Block for Headache after Concussion

Potential participants who are eligible for the study will be identified from a concussion clinic at the University of Michigan and will complete the informed consent process. After enrolling in the study, they will be linked to a daily online survey which will ask them to record daily symptom severity scores using the Sport Concussion Assessment Tool version 5 (SCAT5) symptom checklist, rating symptoms (including headache) on a scale of 0 to 6, with 0 corresponding to “absent” and 6 corresponding to “severe.” They will also be asked to record the number of headache episodes, the number of hours with headache, and the number of doses of as-needed headache medication usage every 24 hours for the one week prior to the research visit.

Participants will take part in one in-person research visit, during which the SPG block procedure will be performed. At the beginning of the visit, participant demographic information and baseline characteristics will be recorded, including age, sex, height, weight, date of concussion, history of baseline migraine, depression, anxiety, or ADHD, and history of previous concussions. The participant also will complete the 22-item SCAT5 symptom checklist, as before. Participants will then be fitted with a chest-worn Polar heart rate monitor, which will record resting heart rate and R-R interval while in the supine position. Heart rate will then be recorded immediately after standing, and after standing for two minutes. Next, the SPG block procedure will be performed, as described below. 15 minutes after the procedure, heart rate and R-R interval will be recorded in identical fashion to the pre-procedure recordings. Finally, the participant will again complete the SCAT5 symptom checklist.

Following the research visit, they will record SCAT5 symptom scores, headache episodes, headache hours, and as-needed headache medication usage every 24 hours for the one week following the research visit, identical to the pre-procedure recordings. Additionally, they will complete the SCAT5 symptom checklist and rate their status on the PGIC scale at two hours post-SPG on the day of the research visit. Their direct participation in this study will conclude after the one week post-SPG block survey data is recorded.

The following detail summarizes the time points and components of data collection during the research study.

	SCAT5	oHR	HRV	HA episodes	HA hours	# PRN doses	PGIC	AEs
Every 24 hours, before the SPG block	x			x	x	x		x
SPG visit (pre-procedure)	x	x	x					x

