### ***8. Statistical Design***

## **A Phase II Randomized Controlled Double-Blind Clinical Trial of Sphenopalatine Ganglion Block for Headache after Concussion**

For the primary outcome, an analysis of covariance (ANCOVA) model will be used to determine treatment effect. The post-treatment headache severity score will be the dependent variable, and the pre-treatment headache severity score and treatment type (lidocaine or placebo) will be independent variables in the model. An ANCOVA model will be used to evaluate for treatment effect in post- vs pre-treatment mean headache severity scores in the 48 hours following the SPG block compared to the 48 hours before the SPG block.

Similar ANCOVA models also will be used to evaluate for between-group treatment effect for the following secondary and exploratory outcomes:

- mean number of days with headache in the one week post-SPG block compared to one week pre-SPG block.
- mean number of headache occurrences within both 48 hours pre- and post-SPG block and one week pre- and post-SPG block
- mean number of headache hours per day within both 48 hours pre- and post-SPG block and one week pre- and post-SPG block
- mean number of as-needed headache treatment uses per day within both 48 hours pre- and post-SPG block and one week pre- and post-SPG block
- mean symptom severity scores in all 22 symptoms on the SCAT5 symptom checklist in both the 48 hours and one week pre-SPG block compared to 48 hours and one week post-SPG block
- mean orthostatic heart rate on standing, and mean orthostatic heart rate change from supine to standing, post-SPG block compared to pre-SPG block
- root mean square of successive differences (RMSSD) post-SPG block compared to pre-SPG block

For the following secondary outcomes, a mixed design analysis of variance (ANOVA) will be used, with a within-subjects factor of time (e.g. pre- vs post-SPG block) and a between-subjects factor of treatment (SPG block with lidocaine vs SPG block with saline):

- mean headache severity score within 15 minutes, 2 hours, 24 hours, and one week post-SPG block compared to immediately prior to procedure, 24 hours, and one week pre-SPG block.
- values on the PGIC rating scale at 2 hours and 24 hours post-procedure in those who received an SPG block with lidocaine compared to a placebo SPG block

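### The baseline SCAT5 precedes the standing heart-rate test but the post-block SCAT5 follows it, so the nominal 15-minute headache rating is taken under different conditions and at 22 minutes or later

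*Combined protocol and SAP*

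**What the plan says.** Section 6.9 (Outcome measures) asks the patient at the visit to "report a headache severity score immediately before the procedure, 15 minutes after the procedure, and two hours after the procedure". Section 8 (Statistical Design) uses these scores in a secondary mixed-design ANOVA of "mean headache severity score within 15 minutes, 2 hours, 24 hours, and one week post-SPG block compared to immediately prior to procedure" and other pre-block times. The schedule table puts the post-block SCAT5, orthostatic heart rate and heart rate variability in a single row labelled 15 minutes.

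Section 6.10 (Schedule of Visits and Testing Requirements) fixes the order of the steps. Before the block: "The participant also will complete the 22-item SCAT5 symptom checklist, as before. Participants will then be fitted with a chest-worn Polar heart rate monitor". The supine recording comes next, and then "Heart rate will then be recorded immediately after standing, and after standing for two minutes". The block follows. After the block, the same heart-rate recordings start at 15 minutes, and only then: "Finally, the participant will again complete the SCAT5 symptom checklist".

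**The concern.** A pre-to-post comparison should hold everything constant except the intervention. Here the baseline symptom rating is made before a change of posture and the post-block rating directly after one. The heart-rate measurements are repeated identically on the two occasions; the symptom rating is not.

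This matters more than usual in this trial because Section 4 (Background) links symptom generation after concussion to autonomic dysfunction, and Exploratory Aim 2 expects lidocaine to reduce abnormal heart-rate rises on standing. On those premises, a score given just after standing may reflect the standing test as well as the block. At stake is the interpretation of the first post-block headache rating, and whether its stated time is right.

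**Working it through.** **Inputs**
- Order of steps: Section 6.10.
- R-R recording, supine: 5 min (6.9). Standing: 2 min (6.9).
- Supine rest after the solution is given: 5 min (6.8). Further monitoring: 10 min (9.2).
- Stated time of the post-block rating: 15 min (6.9 and the schedule table); no later than 15 min (Section 8).

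**Order, side by side**
- Before: SCAT5 → monitor fitted → supine recording → standing → block.
- After: block → wait to 15 min → supine recording → standing → SCAT5.

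**Time of the post-block rating**
- Start of the heart-rate test + supine recording + standing = 15 + 5 + 2 = 22 min at the earliest.
- The 15 minutes appear to include the supine rest, since 5 min (6.8) + 10 min (9.2) = 15 min. If the clock instead started after the rest, the result would be 5 + 15 + 5 + 2 = 27 min.
- The stated 15 min is not reproduced on either reading.

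**Time of the baseline rating**
- Supine recording + standing = 5 + 2 = 7 min before the block at the latest, plus the time to fit the monitor.

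**Is the SCAT5 the source of the visit headache score?** The schedule table has no column for a separate headache severity score, and its footnote says that the SCAT5 includes headache. Section 6.10 lists no other rating at these points.

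**Effect on the comparison.** Let τ be the true difference between arms in change, and s₀ and s₁ the mean shift in the rating from having just stood, on placebo and on lidocaine.
- Change within the placebo arm = true change + s₀, and likewise with s₁ for lidocaine.
- Difference between arms = τ + (s₁ − s₀). It equals τ when s₁ = s₀.

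A simulation used 12 per arm and 20,000 replicates, with assumed values: unit SD, pre/post correlation 0.6, and a t-test on change scores, which is the time-by-treatment test for two time points. The shift was drawn from the same distribution in both arms.

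| Mean shift | SD of shift between participants | Placebo-arm change | Type I error | Power for a 1 SD effect |
|---|---|---|---|---|
| 0 | 0 | 0.00 | 0.051 | 0.746 |
| 0.5 | 0 | 0.50 | 0.052 | 0.742 |
| 0.5 | 0.5 | 0.50 | 0.052 | 0.627 |
| 1.0 | 0.5 | 1.00 | 0.050 | 0.626 |

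The estimated difference between arms stayed at 0.00 under the null and −1.00 for a true −1 throughout. The loss of power comes from the spread of the shift. The SD of change is √(2 − 2 × 0.6) = 0.894 without it and √(0.80 + 0.25) = 1.025 with it, so a 1 SD effect falls from 1/0.894 = 1.12 to 1/1.025 = 0.98 SDs of change.

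**Scope.** The primary ANCOVA uses 48-hour means. The PGIC uses 2 and 24 hours. The SCAT5 ANCOVAs use 48 hours and one week. None of them uses the 15-minute rating.

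**The case against.** The strongest reply is that the planned test is between randomised arms with identical visit order, so a shift common to both cancels. That is correct, and the simulation agrees. A loss of power appears only if the shift is assumed to vary between participants.

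A differential effect needs two things that the documents do not establish: that two minutes of standing changes the headache rating, and that lidocaine alters that response. The second is only an exploratory hypothesis. Even if both held, the difference would still be caused by lidocaine, though not wholly by relief of headache. This stands as a limit on the point. It does not remove it, because the trial itself puts the hypothesis forward.

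It can also be said that 15 minutes is a nominal label: 6.9 applies it to a heart-rate sequence that itself lasts at least 7 minutes, and the table groups all three measurements under it. That softens the mismatch, but Section 8 sets 15 minutes as an upper limit, which 22 minutes does not meet.

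Thirdly, 6.9 could mean a separate headache score taken at the exact times. Neither 6.10 nor the schedule table lists one. If one was intended, both would need correcting.

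Finally, moving the SCAT5 forward might push the heart-rate recording past its own nominal 15 minutes. The existing wait can absorb the checklist, so this need not happen.

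**Conclusion.** The point holds, with narrow scope. The baseline and post-block ratings sit on opposite sides of a standing test, and the post-block rating falls at 22 minutes or later (27 on the less likely clock) against a stated 15. This applies to every participant, but to one time point of one secondary analysis. The timing result rests only on the documents' own step lengths and on the SCAT5 being the source of the visit headache score. The simulated loss of power, from about 0.75 to 0.63, rests on assumed values and illustrates the mechanism only.

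A reader might infer three stronger things that the documents do not support:
- That the two ratings cannot be compared, or that the treatment contrast is biased. A common order effect cancels between arms; bias needs lidocaine to change the response to standing.
- That standing pushes the scores towards worsening. The documents give neither the direction nor the size of any provocation.
- That the baseline rating also misses its stated time. It is at least 7 minutes before the block, but the wording in 6.9 has no defined window and the schedule table says only that the rating is pre-procedure, which it is. This half is arguable.

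**What to change.** In 6.10, have the participant complete the post-block headache score and SCAT5 at the end of the existing 15-minute post-block monitoring period, before the heart-rate sequence starts. Participants sit up after 5 of those minutes, which leaves ten for the checklist. The order then matches baseline, and both the rating and the heart-rate test keep their nominal 15-minute time. In 6.9 and Section 8, describe the baseline visit rating as taken at the start of the visit, before the heart-rate test.

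The cost is the reordering of two steps in one visit and small wording changes in three sections. If the checklist overruns, the heart-rate recording starts a few minutes late, under the same procedure in both arms.

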## A Phase II Randomized Controlled Double-Blind Clinical Trial of Sphenopalatine Ganglion Block for Headache after Concussion

SPG visit (15 min post- procedure)	x	x	x					x
2h post- procedure	x						x	x
24h post- procedure	x			x	x	x	x	x
Every 24 hours, before the SPG block	x			x	x	x		x

- SCAT5: Sport Concussion Assessment Tool version 5, 22-item symptom checklist, including headache; each symptom rated between 0 and 6.
- oHR: Orthostatic heart rates (HR); HR measured while laying supine at rest, immediately after standing, and after standing for two minutes.
- HRV: R-R interval measured while laying supine at rest
- HA episodes: The number of discrete headache episodes of any duration that occurred during the 24 hour period.
- HA hours: The number of cumulative hours with headache during the 24 hour period.
- # PRN doses: The number of doses of as-needed headache treatments (e.g. acetaminophen, ibuprofen) used during a 24 hour period.
- PGIC: Patient Global Impression of Change, 7-item rating scale ("1" = very much improved, "7" = very much worse)
- AEs: Adverse events

### *6.11 Early Withdrawal/Premature Discontinuation of Subjects:*

A participant may voluntarily withdraw from this study at any time, and participants also can be withdrawn from the study at the investigator's discretion. If a participant is withdrawn from the study, their collected data up to the time in which their participation in the study ends will remain included in the study data and will be used for analysis.

### *6.12 Handling of Lost-to-Follow-Up Subjects:*

If a participant does not complete any part of the pre- and post-procedure survey data, the study coordinator will make efforts to contact the participant to complete the missing data. Any correspondence with participants will be documented and maintained as part of the participant's study file.

### *6.13 Sample size and power calculation:*

## **A Phase II Randomized Controlled Double-Blind Clinical Trial of Sphenopalatine Ganglion Block for Headache after Concussion**

Sample size calculations were based on previous studies on the use of SPG blocks in acute migraine headache[11] and chronic migraine,[5] in addition to considering the expected recruitment potential from the clinic in the one year study grant period. A sample size of 24 participants (12 per group) was calculated to achieve 80% power with an alpha cutoff 0.05.

### ***6.14 Randomization***

To achieve two groups with equal numbers balanced by treatment type (i.e. SPG block with lidocaine vs placebo with saline), a block randomization method will be utilized. To maintain blinding, the study coordinator will prepare SPG block materials based on the randomization scheme in advance of the participant study visit.

### ***7. Adverse Events***

Adverse events (Aes) will be queried as part of the daily online survey every 24 hours. Participants also will be encouraged to contact the study team with any concerns for AEs. All AEs, regardless of severity will be recorded and followed by the principal investigator.

#### ***7.1 Anticipated Clinical Signs and Symptoms:***

It is anticipated that during the SPG block procedure, participants may experience brief discomfort when the catheter tip is inserted into the nares. The participant may experience a brief, unpleasant taste sensation from the inserted liquid (either lidocaine or saline solutions). In the case of the lidocaine treatment, participants may experience transient numbness of the nasopharyngeal mucosa. These anticipated signs and symptoms will not be considered AEs and are not expected to lead to any Aes.

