#### ***7.2 Severity of Adverse Events:***

All AEs will be assessed for their severity and will adhere to the UM IRBMED's standard AE adjudication table. AE severity will be classified as follows:

- Minor: An AE of either no consequence requiring no therapy, or of no consequence requiring only nominal therapy (e.g. overnight hospital admission for observation).
- Major: An AE requiring therapy and a non-complicated hospital stay (<48 hours); requiring major therapy or prolonged hospitalization (>48 hours); causing permanent adverse sequelae; causing death.

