### **9. Risks/Benefits**

#### *9.1 Risks:*

Risks related to the procedure are expected to be mild and temporary and include:

- No improvement or worsening of headache
- Allergic reaction to the medication
- Tearing of the eye
- Nose discomfort
- Nose bleeding
- Damage to surrounding structures, including the nasal passage
- Mouth or throat numbness
- Coughing
- Nausea
- Vomiting
- Dizziness
- Light-headedness
- Fainting

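### Section 7.1 takes three expected effects of the block out of the adverse event definition and provides no other place to record them, so any count by arm would omit them, including numbness expected with lidocaine only

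*Combined protocol and SAP*

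**What the plan says.** Section 7.1 lists three things the sponsor expects to happen around the procedure:

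- Discomfort: "participants may experience brief discomfort when the catheter tip is inserted into the nares".
- Taste: a "brief, unpleasant taste sensation from the inserted liquid (either lidocaine or saline solutions").
- Numbness: "In the case of the lidocaine treatment, participants may experience transient numbness of the nasopharyngeal mucosa".

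It then closes with the rule: "These anticipated signs and symptoms will not be considered AEs and are not expected to lead to any Aes".

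Three other places bear on this. Section 7 gives the recording rule: "All AEs, regardless of severity will be recorded and followed by the principal investigator". Section 7.2 sets the lowest severity class, which begins "Minor: An AE of either no consequence requiring no therapy". Section 9.1 lists the risks of the procedure, among them "Nose discomfort" and "Mouth or throat numbness". Taste is not on that list.

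The schedule in Section 6.10 has one AE column, marked at every time point, including 15 minutes, 2 hours and 24 hours after the procedure. It has no column for procedural symptoms. Section 8 lists the between-group analyses, and none of them concerns AEs.

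**The concern.** The rule removes from AE recording the effects that the plan itself expects of the block. If an anticipated effect is not an AE, and the AE query is the only instrument for harms, a team that follows the plan exactly need not write it down at all.

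The frequency, duration and severity of these effects in each arm would then be unknown at the end of the trial. A later study would have a description of them but no incidence.

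Numbness raises a further issue. It is expected with lidocaine and not with saline, and the primary outcome is a self-reported headache score in a double-blind trial. A by-arm record of numbness would help a reader judge how far participants could have guessed their allocation. Under the present rule that record need not exist.

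**Working it through.** The plan states no figure on this point, so there is nothing to reproduce. The check compares passages, with a small illustration of size.

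**Step 1. Is there another place to record the three effects?** Section 6.9 (outcome measures) covers headache, global impression of change, medication use, the SCAT5 checklist and heart rate. The schedule in Section 6.10 adds only the AE column. Sections 7 and 7.3 deal with AEs alone. None provides for recording the excluded effects.

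**Step 2. How does the exclusion fit the rest of the AE framework?**

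| Effect in 7.1 | Limiting word in 7.1 | Arm in which expected | Fits Minor class in 7.2? | Counterpart in 9.1 |
|---|---|---|---|---|
| Discomfort at insertion | brief | both (same insertion) | yes | nose discomfort (not limited to insertion) |
| Unpleasant taste | brief | both (stated) | yes | none |
| Nasopharyngeal numbness | transient | lidocaine only | yes | mouth or throat numbness (neighbouring sites) |

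All three would fall naturally into the Minor class if they were AEs, and two have close counterparts among the listed risks. Neither limiting word has a duration or severity attached, so two assessors could classify the same episode differently.

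**Step 3. What does the omission do by arm?** If discomfort or taste occurs at the same rate q in each arm, leaving it out removes 12q expected participants from each side. The expected difference is 12q − 12q = 0 with or without the exclusion, so absolute counts fall but the contrast need not move. If numbness occurs at rate p with lidocaine and at 0 with saline, leaving it out removes 12p from one side only.

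**Step 4. Illustration for numbness.** The 12 per group comes from Section 6.13. The rates p are assumptions, because the documents give none. The expected number uncounted is 12p.

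To show whether a contrast of this kind could be seen in so small a trial, compare x/12 with 0/12 by Fisher's exact test, two-sided. With x = 4, p-value = 2·C(12,4)/C(24,4) = 2·495/10,626 = 0.093. With x = 5, it is 2·C(12,5)/C(24,5) = 2·792/42,504 = 0.037. So at least 5 participants with numbness are needed, and the chance of reaching 0.05 is P(X ≥ 5) for X ~ Binomial(12, p).

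| Assumed p | Expected uncounted, 12p | Chance of p-value ≤ 0.05 if counted |
|---|---|---|
| 10% | 1.2 | 0.4% |
| 25% | 3 | 16% |
| 50% | 6 | 81% |
| 75% | 9 | 99.7% |

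The test only gives a sense of scale. It is not a proposal to test AEs formally.

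**The case against.** The strongest reply is that this is an openly stated definition and nothing planned depends on it. Much of that reply stands.

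- **Contradiction.** A reader might infer that Sections 7, 7.1 and 9.1 contradict one another. They do not, strictly. Section 7.1 narrows what counts as an AE, and Section 7 then records everything that counts, so both can be followed. Section 9.1 is a list of risks, not of AEs. It includes failure of the headache to improve, so appearing there does not make something an AE. Its two items are also worded more widely than the exclusions, or name different sites.
- **A biased safety comparison.** A reader might infer that the trial's safety comparison will be understated. Section 8 plans no such comparison, and the objectives and aims name no safety endpoint. The stated uses of AE data are follow-up and grading by the principal investigator, reporting to the IRB, and regular review by the study group.
- **Longer episodes lost.** The exclusion covers only brief or transient effects. A symptom that persisted would meet repeated AE queries after the procedure. The missing limit leaves an ambiguity at the boundary, but it does not mean that prolonged events go unrecorded.
- **Prompting.** Asking every participant about numbness shortly after the procedure could encourage guessing of allocation while the 48-hour self-reported outcome is still being collected. This is a real cost, and the fix has to allow for it.

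None of this supplies a place to record the three effects. The gap comes from a stated rule, so it is more than a missing detail.

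**Conclusion.** The point holds in a limited form. Section 7.1 excludes three expected effects and the plan records them nowhere else, so any AE tabulation by arm would omit them. For discomfort and taste the loss is in absolute counts, and a contrast between arms need not be biased. For numbness the loss falls on the lidocaine arm alone.

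The size cannot be derived from the documents. Under assumed rates of 10% to 75% it is about 1 to 9 of 12 lidocaine participants. At the low end an arm difference would hardly ever be visible in this trial, and at 50% or more it usually would be. These figures assume no numbness with saline and full enrolment of 12 per arm.

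No stated objective or planned analysis changes as a result. What suffers is the completeness of the harms record, and with it one piece of evidence on blinding. The change is worth making because it is cheap.

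**What to change.** Replace the closing sentence of Section 7.1 with a rule of this kind: insertion discomfort, unpleasant taste and nasopharyngeal numbness are recorded as expected events, with duration and severity, within the existing AE query, and are reported by arm. Add to Section 8 a descriptive summary of AEs and expected events by arm, without formal testing.

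To protect the blind:

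- use a neutral checklist, identical in both arms;
- record spontaneous reports of any symptom when they occur;
- put any direct question about numbness only after the 48-hour headache ratings are complete.

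The expected events may stay exempt from expedited IRB reporting. Sections 7, 7.1, 7.2 and 9.1 should be reconciled so that they use the same terms and sites. The sponsor should also state when an effect ceases to be brief or transient and becomes an ordinary AE.

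The cost is a few survey items and a few table rows. The reported AE rate will look higher, which a separate heading for expected events can explain. Asking about numbness later means less precise recall of a short-lived symptom, which is the price of not drawing attention to it while the primary outcome is being rated.
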